6.6.4. Digital Reading Index and Visual Function Application

The digital reading index will only be analyzed at the Month 24 reporting while the digital visual functional application will be analyzed at both the Month 12 and Month 24 reporting.

Descriptive summary statistics for baseline, absolute values, and change from baseline data to Month 12 and Month 24 will be provided by treatment group for digital reading index.

Additionally, the average digital reading index score over the last 3 months for each reporting period (Month 10 - Month 12 for the Month 12 reporting; Month 22 - Month 24 for the Month 24 reporting) will be calculated for each subject who has at least one digital reading index assessment in these windows. The observed values for the digital reading index and changes from baseline will be summarized by treatment group. Summaries will present the descriptive statistics for baseline, absolute values and change from baseline data.

Descriptive summary statistics for baseline, absolute values and change from baseline data to Month 12 and Month 24 will be provided by treatment group for digital visual function.

Additionally, the average digital visual function score over the last 3 months for each reporting period (Month 10 - Month 12 for the Month 12 reporting; Month 22 - Month 24 for the Month 24 reporting) will be calculated for each subject who has at least one digital visual function assessment in these windows. The observed values for the digital visual function and changes from baseline will be summarized by treatment group. Summaries will present the descriptive statistics for baseline, absolute values and change from baseline data.

6.6.5. Genetic Polymorphisms

The genetic polymorphisms data will be analyzed and reported in a separate report and briefly summarized in the clinical study report (CSR). The genetic polymorphisms data will be listed for the genotyping set.

6.6.6. Dry AMD Analysis

Biomarkers of early and intermediate stage of AMD outside the GA area will also be evaluated in this study. The number and percentage of subjects with at least one lesion (up to 5) area in the study eye classified as iRORA will be summarized at baseline by treatment group in the mITT set. The number and percentage of subjects with a progression from iRORA to cRORA based on SD-OCT in the study eye will be summarized over time by treatment group. A CMH test with the number of baseline iRORA lesions (0, 1, 2, 3, 4, ≥ 5), presence of CNV in the fellow eye (yes or no), and baseline GA lesion area ($< 7.5 \text{ mm}^2$ or $\geq 7.5 \text{ mm}^2$) as the stratification factors will be presented for each post-baseline visit. If necessary due to sparse cells, an unadjusted analysis may be performed. In addition, the percentage of baseline lesions with a progression will also be presented over time by treatment group.

The above summary and analysis will also be repeated in those subjects with at least one lesion in the study eye classified as large drusen at baseline and whether these progressed to iRORA or cRORA in the study eye. Large drusen is defined as a drusen that is greater than or equal to 40 microns in height on SD-OCT.

This analysis will not be conducted at the Month 12 reporting and will only be conducted for the final study reporting.

All dry AMD data will be listed for the ITT set.

6.6.7. Analyses of Other Ophthalmology Efficacy Imaging Data

In addition to the GA lesion(s) size data from the FAF, analysis of additional efficacy parameters will be performed from this imaging instrument for the mITT set. The following summaries will be performed separately by study eye and by fellow eye and will be presented by treatment group.

- Descriptive summary statistics for baseline, absolute values and change from baseline data for the distance of GA lesion from atrophy junction to the fovea in study eyes with non-subfoveal involvement of the GA lesion at baseline (assessed from FAF). For the fellow eye, this will be presented for fellow-eyes with non-subfoveal involvement of the GA lesion at baseline. Non-subfoveal involvement is defined as distance of the atrophy junction to the fovea > 0 .
- Conversion from non-subfoveal involvement to subfoveal involvement of the GA lesion at each visit (assessed from FAF). This will include only study eyes with non-subfoveal involvement for GA lesions at baseline. For the fellow eye, this should be presented for fellow eyes with non-subfoveal involvement at baseline. This will be presented as a cumulative incidence at each scheduled visit.

All FAF data will be listed for the ITT set.

7. SAFETY ANALYSES

Safety analyses will be performed using the Safety set. Safety variables include adverse events (AEs), deaths, clinical laboratory results, vital signs, incidence of ADA against pegcetacoplan, ocular assessments (e.g., NL-BCVA, IOP and ophthalmic examinations), and ocular imaging.

At the time of the Month 12 reporting, safety summaries will be produced based on the complete Month 12 data. At the time of the final study reporting, safety summaries will be produced based on cumulative data.

For each safety variable, the last value collected before the first dose of investigational product will be used as baseline for all analyses of that safety variable. Last Observed Value (LOV) will be defined as the last valid assessment obtained after baseline. The LOV will be presented for the Month 12 reporting as well as the final study reporting.

All safety analyses will be conducted according to the actual treatment the subject received. Unless otherwise specified, all safety summaries will be performed on the Safety set.

7.1. Adverse Events

AEs will be coded using the MedDRA version 23.1 and summarized separately for those occurred in the study eye, those in the fellow eye, and the non-ocular events.

An AE will be considered a TEAE if it has a start date on or after the first dose of investigational product or if it has a start date before the date of the first dose of investigational product but increases in severity on or after the date of the first dose of investigational product.

An overall summary of the number of subjects with TEAEs will be presented, including the number and percentage of subjects with:

- Any TEAEs
- TEAEs related to study drug (evaluated by the investigator as definitely related, possibly related)
- TEAEs related to study drug injection procedure
- All TEAEs by maximum severity
- Serious TEAEs
- Serious TEAEs related to study drug (evaluated by the investigator as definitely related, possibly related)
- Serious TEAEs related to study drug injection procedure
- Serious TEAEs by maximum severity
- TEAEs leading to interruption of study treatment
- TEAEs leading to discontinuation of study treatment
- TEAEs leading to study discontinuation
- TEAEs leading to death

This overall summary will also include the total number of TEAEs reported. This overall summary will also be summarized separately for those occurred in the study eye, those in the fellow eye, and the non-ocular events.

The number and percentage of subjects reporting TEAEs in each treatment group and overall will be tabulated by SOC and PT for all of the categories in the list above. If more than 1 AE occurs with the same preferred term for the same subject, then the subject will be counted only once for that preferred term using the most severe and most related occurrence for the summarization by severity and by relationship to investigational product.

Endophthalmitis and intraocular inflammation ocular TEAEs will be presented by PT for study eye and fellow eye.

Endophthalmitis and intraocular inflammation ocular TEAEs in the study eye will also be presented on a per-injection basis (i.e., number of events/total number of injections given).

All SOC and PT summaries will be ordered alphabetically by SOC and within SOC, by descending order of the total number of subjects in the PM, PEOM, and Sham groups combined.

Non-ocular AEs, ocular AEs in the study eye, and ocular AEs in the fellow eye will be listed separately. This presentation will be repeated for serious AEs. Additionally, separate listings for deaths, AEs leading to discontinuation of study, AEs leading to discontinuation of study drug, and AEs due to COVID-19 will also be generated.

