#### 11.3.1. Relationship of Events to Study Treatment

All AEs that occur during this study will be recorded. The investigator will review each event and assess its relationship to study treatment (definitely related, possibly related, unlikely related, not related, unknown). The date and time of onset, time relationship to drug dosing, duration, and outcome (recovered/resolved, recovered/resolved with sequelae, recovering/resolving, not recovered/not resolved, fatal, or unknown) of each event will be noted.

The following definitions should be considered when evaluating the relationship of AEs and SAEs to the study treatment:

Definitely Related	
 
• Event or laboratory test abnormality, with plausible time relationship to drug intake
 
• Cannot be explained by disease or other drugs
 
• Response to withdrawal plausible (pharmacologically, pathologically)
 
• Event definitive pharmacologically or phenomenologically (ie, an objective and specific medical disorder or a recognized pharmacological phenomenon)
 
• Rechallenge satisfactory, if necessary
 

Possibly Related	
 
• Event or laboratory test abnormality, with reasonable time relationship to drug intake
 
• Could also be explained by disease or other drugs
 
• Information on drug withdrawal may be lacking or unclear
 

Unlikely Related	
 
• Event or laboratory test abnormality, with a time to drug intake that makes a relationship improbable (but not impossible)
 
• Disease or other drugs provide plausible explanations
 

Not Related	
 
• Event or laboratory test abnormality, is plausibly related to the participant's clinical state, underlying disease, or the study procedure/conditions
 
• Time relationship to drug intake makes a relationship unreasonable
 
• Other obvious causes for event or laboratory test abnormality exist
 

Unknown	
 
• Report suggests an adverse event, however, cannot be judged at this time because information is insufficient or contradictory
 
• More data for proper assessment is needed, or additional data is under examination
 

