13.7.5. Missing Relationship to Investigational Product for Adverse Events

If the relationship to investigational product is missing for an AE starting on or after the date of the first dose of investigational product, a causality of "Related" to the investigational product will be assigned. The imputed values for relationship to double-blind investigational product will be used for incidence summaries, while both the actual and the imputed values will be presented in data listings.

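### A TEAE with causality recorded as Unknown falls outside the related-event rows, while one with causality left blank counts as related

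*SAP*

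**What the plan says.** Protocol 11.3.1 asks the investigator to review each event and "assess its relationship to study treatment (definitely related, possibly related, unlikely related, not related, unknown". Each of the five values has its own definition. For Unknown, the definition includes: "Report suggests an adverse event, however, cannot be judged at this time because information is insufficient or contradictory".

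SAP 7.1 lists the rows of the overall TEAE summary. One is "TEAEs related to study drug (evaluated by the investigator as definitely related, possibly related", and a second applies the same two values to serious events: "Serious TEAEs related to study drug (evaluated by the investigator as definitely related, possibly related". The same section asks for SOC/PT tables for every category in that list. It counts a subject once per preferred term, using the most severe and most related occurrence. SAP 7.1.1 repeats the overall summary for Exudative AMD TEAEs in the study eye.

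SAP 13.7.5 covers absent causality. Its trigger is "If the relationship to investigational product is missing for an AE starting on or after the date of the first dose of investigational product", and the assigned value is Related. It adds: "The imputed values for relationship to double-blind investigational product will be used for incidence summaries". Listings show both actual and imputed values.

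**The concern.** An Unknown code and a blank field tell the analyst much the same about causality: nobody has judged the event related or unrelated. The SAP sends them to opposite sides of the related-event rows and does not say why.

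The split also runs against how the SAP treats absent AE information elsewhere. Unless something contradicts it, an event with an unclear date is taken as treatment emergent (13.7.3). Missing severity on an event starting on or after first dose becomes Severe (13.7.4). Missing causality becomes Related (13.7.5). Unknown causality is the one state of ignorance that does not default in the cautious direction.

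At stake are the related and serious related rows, which readers of a safety report look at closely. The Exudative AMD summary inherits the same definition. Protocol 4.1.4 reports a Phase 2 imbalance in new active CNV (25/165 on pegcetacoplan against 1/81 on sham), so that table will be read with care.

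**Working it through.** The plan gives no figure to reproduce here. The check follows each value that can be recorded through the SAP's rules.

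**Step 1: mapping for an event starting on or after first dose.**

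| Causality on the form | Source of the rule | In the related rows? |
|---|---|---|
| Definitely related | SAP 7.1 list | Yes |
| Possibly related | SAP 7.1 list | Yes |
| Unlikely related | Not in SAP 7.1 list | No |
| Not related | Not in SAP 7.1 list | No |
| Unknown | Not in SAP 7.1 list; recorded, so not missing under 13.7.5 | No |
| Blank | SAP 13.7.5 assigns Related | Yes |

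No other SAP section maps Unknown, gives it a row of its own, or ranks it for the per-term rule. Section 15 (changes from the protocol) does not address it.

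**Step 2: direction.** Handling Unknown like a blank can only add subjects to the related rows or leave them as they are. Relative to the 13.7.5 rule, the counts as planned are therefore too low or equal, never too high.

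**Step 3: which subjects move.** The tables count subjects, not events.
- In the overall related row, a subject moves only if he or she has an Unknown event and no other TEAE that already counts as related.
- In a preferred-term row, a subject moves only if no occurrence of that term already counts as related.
- The serious and Exudative AMD rows follow the same logic within their own sets of events.

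**Step 4: scale.** Protocol Table 1 gives about 200 subjects in each pegcetacoplan arm and about 100 + 100 = 200 in the two sham arms together. Each subject who moves changes the percentage by 1/200 = 0.5 points. The documents give no frequency for Unknown, so the number of such subjects has to be assumed:

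| Subjects who move, in an arm of about 200 | Change in the related percentage |
|---|---|
| 0 | 0 |
| 1 | 1/200 = 0.5 points |
| 10 | 10/200 = 5.0 points |

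**Step 5: what does not move.** The any-TEAE, maximum-severity, total serious, interruption, discontinuation and death rows do not use drug causality and stay the same.

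**The case against.** The strongest defence is that Unknown is an answer and a blank is not. SAP 13.7.5 sits in the section on missing and spurious data, and SAP 7.1 reports what the investigator evaluated. Recoding a recorded answer as Related overrides that evaluation. This would carry weight if Unknown were a view on causality. By the protocol's own definition it is the lack of one, "cannot be judged at this time because information is insufficient or contradictory", and the protocol keeps it apart from Unlikely and Not Related. The inconsistency with 13.7.5 remains.

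The second argument is that Unknown is provisional. Events are followed up (protocol 11.5) and data are queried and cleaned (protocol 12.2, SAP 3.5), so few such codes may be left at lock. That stands, and it is why the effect may be zero. The documents do not guarantee it.

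Third, protocol 12.8 has a tabulation of related events restricted to the definite category, so the SAP is already the broader document. That is true, and SAP section 1 says the SAP's analyses supersede the protocol's. It does not settle how Unknown should be handled within the SAP.

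Three stronger readings are tempting, and the documents do not support them:

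- A reader might infer that related counts are too low by the share of all TEAEs coded Unknown. The tables count subjects, and an Unknown event changes nothing for a subject already counted as related in that row.
- A reader might infer that the control-based imputation in SAP 6.2.3.1 misclassifies the same events. That rule already takes in every discontinuation for an ocular event, whatever its causality, and every one related to the injection procedure. At most it leaves open a non-ocular, non-procedure discontinuation coded Unknown, in an active arm, with later data missing.
- A reader might infer a bias in favour of pegcetacoplan. Unknown is left out of the related rows in every arm, the unmasked injecting staff do not assess adverse events (SAP 3.3), and nothing indicates that Unknown will be used unevenly.

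**Conclusion.** The point holds as a small inconsistency in the safety tabulations. Under the SAP as written, a TEAE with causality recorded as Unknown is outside the related and serious related rows, and the same event with causality left blank is inside. The SAP never says in words that Unknown means unrelated, and it plans no table of unrelated events. The exclusion follows from the closed list in 7.1 together with a rule in 13.7.5 that reaches only missing values.

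The direction is certain relative to the SAP's own missing-causality rule: understated or unchanged. The size is not. It depends on how many Unknown codes survive to lock and on how many of those subjects have no other qualifying event. The range of 0.5 to 5.0 points rests on an assumed 1 to 10 such subjects in an arm of about 200, and zero is possible. Separately, the most-related-occurrence rule cannot be fully programmed until Unknown has a rank. The point does not touch any efficacy conclusion in the main analyses.

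**What to change.** In SAP 7.1 and 13.7.5, state that Unknown causality on an event starting on or after first dose is handled as missing causality. It then counts as Related in incidence summaries and is ranked accordingly when the most related occurrence per preferred term is chosen. Show the recorded category in the listings, where 13.7.5 already requires actual and imputed values side by side. For SAP 6.2.3.1, a cross-reference to this rule is enough.

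The cost is a sentence in each section and a small programming change, with no new data collection. Related and serious related counts may rise slightly in all arms, including sham.

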7.1.1. TEAEs of New Onset Exudative AMD

For subjects who experience a TEAE of “Choroidal neovascularization” or “Neovascular AMD” (“Exudative AMD TEAE”), the following summaries will be performed:

- The overall summary table described in Section 7.1 will be repeated replacing “TEAEs” with “Exudative AMD TEAEs”. This will be reported for the study eye.
- The incidence of Exudative AMD TEAEs in the study eye will be presented by treatment group and overall. In addition, the analysis will be repeated by fellow eye CNV status at baseline and study eye DLS on SD-OCT at baseline. A similar analysis will be repeated for the Exudative AMD TEAEs in the fellow eye with an additional analysis by fellow eye DLS on SD-OCT at baseline. Subjects with a medical history of CNV in the corresponding eye will be excluded from the analysis.
- The incidence and rate per 100 subject-years of Exudative AMD TEAEs in the study and fellow eye as well as a summary (for study and fellow eye) and Kaplan Meier plot for the time to development of Exudative AMD TEAEs in the study eye will be presented by treatment group and overall. Subjects with a medical history of CNV in the corresponding eye will be excluded from the analysis.
- In addition, the characteristics of the Exudative AMD TEAEs in the study eye will be presented at baseline, study visit preceding exudation, study visit at exudation and at Month 12 (or Month 24 if the final analysis) for characteristics based on SD-OCT and baseline, study visit at exudation and at Month 12 (or Month 24 if the final analysis) for characteristics based on Fluorescein Angiography (FA). The following characteristics will be presented by treatment group and overall:

- Presence of cystoid spaces on SD-OCT
 - Central (center point) retinal thickness on SD-OCT
 - Central subfield thickness on SD-OCT
 - Presence of CNV on FA.
 - CNV type on FA
 - Presence of subretinal fluid on SD-OCT
- A summary of concomitant anti-VEGF therapy for new exudative AMD in the study eye will be provided by treatment group and overall. This summary will include the total number of subjects that received any anti-VEGF for new exudative AMD as well as the average number of injections per month post exudative AMD. There will also be a breakdown by preferred term of ranibizumab or aflibercept and the average number of injections per month for each term. Subjects will be presented by the number of injections received for that medication.
 - BCVA scores at the baseline visit, study visit preceding exudation, the study visit at the exudation, and at Month 12 (or Month 24 if the final analysis) will be presented for all subjects with an Exudative AMD TEAE in the study eye by treatment group and overall. In addition, the change in BCVA scores from baseline, the visit prior to the exudation, and the exudation visit will be presented where appropriate.

A listing of Exudative AMD TEAEs and baseline characteristics including fellow eye CNV status, study eye double layer sign and study eye MNV presence, a listing of the characteristics of the new Exudative AMD TEAEs, anti-VEGF exposure, and the BCVA values for subjects with the new Exudative AMD TEAEs will be provided.

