This study demonstrated a statistically significant slowing of disease progression at Month 12 at the prespecified alpha of 0.1. Pegcetacoplan administered monthly showed a 29% ( $P=.008$ ) reduction in the rate of GA lesion growth compared to sham, and pegcetacoplan administered EOM showed a 20% ( $P=.067$ ) reduction. Pegcetacoplan has been generally well tolerated. The most frequently reported AEs have been related to the injection procedure (IVT injection), which are commonly found in this type of study. An imbalance in new active choroidal neovascularization (CNV) in subjects treated with pegcetacoplan was observed and the risk of developing new exudation may be increased in subjects with a prior history of neovascular AMD in the fellow eye. One subject in the sham arm, 1/81 (1%) was observed to have developed new active study eye exudation compared with 25/165 (15%) subjects that received pegcetacoplan IVT injections, 26 subjects in total. Of the 25 pegcetacoplan treated subjects with new active CNV, 18 subjects received PM treatment and 7 subjects received pegcetacoplan every other month (PEOM) treatment.

Seventeen of the 25 (68%) subjects that developed new active study eye CNV had a prior history of neovascular AMD in the nonstudy fellow eye. No significant imbalance in history of neovascular AMD in the fellow eye was observed among the 3 arms to explain the imbalance in new exudation observed in study eyes. Visual acuity data did not demonstrate clear differences between subjects developing new study eye exudation compared with those that did not.

A Phase 1b study (Protocol APL2-103; NCT 03777332) to assess the safety of pegcetacoplan in subjects with GA secondary to AMD and low vision is currently ongoing. This study is being conducted at multiple ophthalmology clinical sites across the US. Subjects receive monthly treatment with IVT pegcetacoplan for 24 months.

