2.1.4. Safety Objectives

To evaluate the safety and tolerability of pegcetacoplan compared to sham injection in subjects with GA secondary to AMD as indicated by:

- Incidence and severity of ocular and systemic treatment-emergent adverse events (TEAEs)
- Incidence of anti-drug antibodies (ADA) directed against pegcetacoplan peptide or polyethylene glycol (PEG)
- Incidence of new active choroidal neovascularization (CNV) in the study eye

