3.2. Randomization

Subjects will be randomized 2:2:1:1 using a web-based randomization system to receive treatment with PM, PEOM, SM or SEOM, respectively.

The randomization scheme will be maintained by the Sponsor, or designee. Subject randomization will be stratified by GA lesion area at screening based on assessment from the reading center ($< 7.5 \text{ mm}^2$; $\geq 7.5 \text{ mm}^2$) and presence of CNV in the fellow eye (yes; no).

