7.7. Other Ophthalmology Imaging Assessments

Unless otherwise stated, ocular imaging data collected will be listed by treatment group and overall for the Safety set. The summary will be performed separately by study eye and by fellow eye. The ophthalmology imaging assessments performed in this study include the following:

- Digital Color Fundus Photographs (DCFP)
 - Shift from baseline in the presence/absence of hemorrhage at each visit
- FA
 - The following analyses will be performed in all study eyes and in non-study eyes without a history of CNV at baseline (in medical history) in the corresponding eye.
 - Incidence of new CNV. This will be summarized as the cumulative number of CNV events by each visit and the cumulative incidence by that visit based on Kaplan Meier methods.
 - Incidence of new CNV by type (classic, occult, classic & occult, disciform scar) at first emergence will be summarized at each visit for the cumulative number of events.
 - Total CNV size (diameter) at first emergence will be summarized at each visit for the cumulative number of events.
- SD-OCT
 - Descriptive statistics on central subfield thickness at each visit
 - Plot of the mean change from baseline in central subfield thickness in the study eye \pm the standard error over time by treatment group.
 - Descriptive statistics on central (center point) retinal thickness at each visit
 - Shift from baseline in the presence/absence of subretinal fluid at each visit
 - Shift from baseline in the presence/absence of cystoid spaces at each visit
- Specular Microscopy

- Endothelial Cell Count is assessed using specular microscopy, and the change from baseline in cell density (cells/mm²) as well as the change from baseline in average cell-size will be summarized with descriptive statistics.
- OCT-A
 - Incidence of subclinical CNV (referred to as MNV in the datasets) determined by OCT-A in eyes without previous CNV reported in the medical history or as an adverse event in the corresponding eye at each visit.

In addition, the following summary of suspected and reading-center confirmed CNV cases will be presented by treatment group. This will be presented separately for the study eye only.

- The number and percentage of subjects with an Exudative AMD TEAE on or before Month 12 (or Month 24 if the final analysis)

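### The SAP shows new exudative AMD and CNV arm by arm but plans no difference from sham and no confidence interval, although the safety objective is comparative

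*SAP*

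**What the plan says.** The safety objective in SAP 2.1.4 is "To evaluate the safety and tolerability of pegcetacoplan compared to sham injection in subjects with GA secondary to AMD as indicated by" several indicators, one of which is "Incidence of new active choroidal neovascularization (CNV) in the study eye". Protocol 5.1.4 says the same.

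SAP 7.1.1 is the dedicated analysis:
- On incidence: "The incidence of Exudative AMD TEAEs in the study eye will be presented by treatment group and overall".
- It then adds that "the analysis will be repeated by fellow eye CNV status at baseline and study eye DLS on SD-OCT at baseline".
- It plans the "rate per 100 subject-years of Exudative AMD TEAEs in the study and fellow eye", a time-to-event summary and a Kaplan-Meier plot for the study eye.
- It describes lesion characteristics, anti-VEGF use and BCVA around the event.

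SAP 7.7 covers imaging. For new CNV on fluorescein angiography it plans cumulative counts and the "cumulative incidence by that visit based on Kaplan Meier methods". It also plans the incidence of subclinical CNV on OCT-A and counts of suspected, confirmed and unconfirmed cases against reported events.

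No default elsewhere adds a contrast. SAP 13.1 gives categorical variables frequencies and percentages. Protocol 12.8 presents adverse events separately for each treatment group. SAP 10 plans no other analyses.

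Protocol 4.1.4 gives the background: "25/165 (15%) subjects that received pegcetacoplan IVT injections" developed new active exudation in the study eye, against 1/81 (1%) on sham. Of the 25 cases, 18 were on PM and 7 on PEOM, and 17 (68%) had a history of neovascular AMD in the fellow eye. Fellow-eye CNV is one of the two randomisation strata (SAP 3.2).

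**The concern.** The objective asks how drug compares with sham. For a harm already seen in Phase 2, the natural answer is an excess risk with its uncertainty, and no planned output gives one.

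Other parts of the SAP do compare arms. Lesion growth gets model-based differences between all three arms with 95% CIs (SAP 6.2.2). Progression from iRORA to cRORA, an exploratory endpoint, gets a CMH test stratified by fellow-eye CNV and lesion area (SAP 6.6.6). New exudation gets neither an estimate nor a test.

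Two statements are at stake: the excess risk of each regimen over sham, and how the two regimens differ. The second matters because Protocol 4.1.6 uses the two frequencies to assess dose response and sets the slightly lower efficacy of EOM dosing against its lower burden. Fixing the method now also avoids choosing it once the counts are known.

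**Working it through.** **1. Phase 2 figures (Protocol 4.1.4).** 25/165 = 15.2%, 1/81 = 1.2%, 17/25 = 68%, and 18 + 7 = 25. All reproduce. The implied difference is 15.2 - 1.2 = 13.9 points before rounding, with a Newcombe 95% CI of 6.8 to 20.3. The risk ratio is 12.3 (1.7 to 89). The ratio is poorly determined because sham has one event.

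**2. What the added table would show.** The design has 200 on PM, 200 on PEOM and 200 on pooled sham (SAP 3.4). The documents state no Phase 3 exudation rates, so the rates below are assumptions. Sham is set at 1% (2/200). Phase 2 denominators by regimen are not given; if the 165 split about evenly (PM n = 76 to 89), PM was 20 to 24% and PEOM 8 to 9%.

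The Newcombe interval uses the Wilson limits (l, u) of each arm:
- lower = d - sqrt((p1 - l1)² + (u0 - p0)²)
- upper = d + sqrt((u1 - p1)² + (p0 - l0)²)

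Example, 30/200 vs 2/200. The Wilson limits are 0.1071 to 0.2061 and 0.0027 to 0.0357.
- Lower: 0.14 - sqrt(0.0429² + 0.0257²) = 0.090
- Upper: 0.14 + sqrt(0.0561² + 0.0073²) = 0.197

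| Assumed risks | Difference (points) | 95% CI |
|---|---|---|
| 22% vs 1% (near Phase 2 PM) | 21.0 | 15.2 to 27.3 |
| 15% vs 1% (Phase 2, both regimens) | 14.0 | 9.0 to 19.7 |
| 8.5% vs 1% (near Phase 2 PEOM) | 7.5 | 3.5 to 12.2 |
| 5% vs 1% | 4.0 | 0.6 to 8.0 |
| 4% vs 1% | 3.0 | -0.2 to 6.8 |
| PM 22% vs PEOM 8.5% | 13.5 | 6.5 to 20.5 |

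For the last row the Wilson limits are 0.1682 to 0.2824 and 0.0537 to 0.1319, so the lower limit is 0.135 - sqrt(0.0518² + 0.0469²) = 0.065.

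**3. Does stratification change the answer?** A Mantel-Haenszel difference was computed with 20 to 40% of subjects having fellow-eye CNV (assumed), equal shares in both arms, 68% of active cases in that stratum and one sham event per stratum. It gives 14.0 (8.9 to 19.1) and 7.5 (3.4 to 11.6). The crude Wald interval for 15% vs 1% is 14.0 ± 1.96 × sqrt(0.15 × 0.85/200 + 0.01 × 0.99/200) = 14.0 ± 5.1, also 8.9 to 19.1.

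Equal shares make the point estimates agree by construction, so imbalance needs its own check. Phase 2 risk on drug would be 17/(165 × 0.2) = 52% with and 8/(165 × 0.8) = 6% without fellow-eye CNV at 20% prevalence, or 26% and 8% at 40%. A 2-point imbalance then moves an arm's risk by 0.02 × 46 = 0.9 or 0.02 × 18 = 0.4 points, which is small against a half-width of about 5.

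**4. Schedule-matched contrasts.** Each sham arm has about 100 subjects (Protocol Table 1). PEOM 17/200 vs SEOM 1/100 (Wilson 0.0018 to 0.0545) gives 7.5 points, with lower limit 0.075 - sqrt(0.0313² + 0.0445²) = 0.021 and upper limit 0.075 + sqrt(0.0469² + 0.0082²) = 0.123. It is wider than against pooled sham but still informative.

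**The case against.** **The plan is already fuller than raw percentages.** This stands. Exposure-adjusted rates, Kaplan-Meier displays, breakdowns by fellow-eye CNV and double-layer sign, and a cross-tabulation of reported against confirmed cases are all planned. They remain displays of single arms, however, and separate rates by stratum are not a treatment contrast.

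**Descriptive safety tables are normal, and neither document promises inference.** This also stands. The point is an omission and not a contradiction, and showing concurrent arms together meets the objective's wording literally. The case for more rests on this being a harm identified before the trial.

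**A reader might infer that the trial cannot state the excess risk.** The documents do not support that. Arm incidences and set sizes are planned outputs, so a crude difference and interval can be worked out from them. The plan simply does not commit to reporting one.

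**A reader might infer that crude contrasts would be distorted by the chance mix of fellow-eye CNV.** Randomisation is stratified on that factor, and the check above shows that a small residual imbalance hardly matters. The reason to stratify is to match the design.

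**A reader might call fellow-eye CNV the main risk factor.** Protocol 4.1.4 says only that risk may be increased. It gives the factor's share among cases and not its prevalence, so no relative risk follows.

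**Ratios and year 2 need care.** This stands. With one or two sham events a rate or hazard ratio may be unstable. In Months 13-24 EOM subjects attend every other month (Protocol 8.1.4.2), so detection opportunity differs by schedule.

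The DMC reviews unmasked data under its own charter and analysis plan (SAP 12), which are not among these documents. That monitoring does not replace an interval in the study report.

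**Conclusion.** The omission is real: neither document plans a between-arm estimate or interval for new exudative AMD or CNV in the study eye. Nothing is lost irrecoverably and no planned result is wrong, so this is a free improvement.

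Its value depends on the true rates. If Phase 2 repeats (about 15% vs 1%), the excess is plain without an interval. The interval matters most for a modest excess, where 5% vs 1% has a lower limit of 0.6 and 4% vs 1% crosses zero, and for PM against PEOM, where the half-width is about 7 points. These figures assume 200 per group, 1% on sham and the stated active rates, none of which the documents give for this trial.

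**What to change.** In SAP 7.1.1 add one table for the study eye, through Month 12 and through Month 24, in the Safety set:
- Risk difference with 95% CI for PM vs pooled sham, PEOM vs pooled sham and PM vs PEOM.
- A score-type interval suited to near-zero sham counts, stratified by fellow-eye CNV (for example stratified Miettinen-Nurminen or stratified Newcombe).
- Descriptive, with no alpha.
- At Month 24, also PM vs SM and PEOM vs SEOM, with a note that PM vs PEOM then mixes risk with detection opportunity.
- A rate or hazard ratio as supportive only, and only if event counts allow.

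Apply the same to reading-centre confirmed CNV in SAP 7.7.

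Cost: one extra table for each of the two definitions of the event, from data and a stratification factor already collected. No change to sample size, visits or the testing strategy.
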